6.7 Qualitative data

16

Qualitative work will focus on two groups: (a) teachers and (b) parents/children

(a) Teachers attitudes and the value the place on the intervention will be to better understand what worked well, what created barriers and look at how best to support implementation for such initiatives in the future if appropriate.

In a qualitative approach, we will explore the teachers' attitudes, and opinions regarding the multi component intervention. A combination of focus groups and one-to-one interviews (depending on availability) will take place with teachers and staff within

schools. We will aim for interviews to include at least 15 teachers. Data saturation will be monitored throughout, and data collection will cease when saturation is reached.

Parents attitudes and opinions regarding the interventions be explored through a qualitative, semi-structured approach. A similar approach as with dental teams will be followed where parents of children will be invited to an interview to understand what, in their experience, worked well with the multi component intervention, if there were any barriers and shortcomings in their experience and if anything could be improved. We aim for 15 interviews to be completed with parents. Data saturation will be monitored throughout, and data collection will cease when saturation is reach

For children, given their age, a different approach to understand their experiences and provide them with a chance to hear their voices and opinions will be utilised. Children will be asked for their opinions on the different components of the intervention, but they will also be offered the opportunity to produce a picture of their experience and the parts they remember for the intervention. Asking children of a certain age to populate and communicate their experiences using art is not new but it is rarely used within healthcare research (20). The benefits of this approach can be multiple from offering children a platform to share their experiences to helping with the dissemination of findings through visual and artistic approaches. In total, we aim for at least 5 children to engage in this process and share their experiences.

While written consent will be obtained to take part in the clinical part of the study, qualitative interviews consent will be obtained from participants through a verbal consent script prior to the commencement of any interview questions. Participants will be asked to clearly state their names in the audio recording following a comprehensive explanation of the study's objectives and the purpose of the interview, which would be read aloud individually by the research staff and provided to participants in a clear and concise language. Participants will be asked to confirm "Yes" or "No" to taking part in the interview with additional points will be clearly stated. Prior to soliciting consent, participants will undergo a confirmation of understanding to ensure comprehension of the study's aims and importance of their response. Only after this confirmation will verbal consent be sought for participation in the qualitative interview. Additionally, participants will be informed of their right to refuse participation or withdraw consent at any point during the interview process. The verbal consent process will be thoroughly documented, including the date of consent, and confirmation of the participant's agreement to participate. Alternatively, written consent can also be sought if requested by participants. Participants who consent to partake in the interview will be sent a hard copy of the consent form via email or post. Qualitative interviews will be recorded on a recording device. Information shared by consented participants will only be used for research purposes, Audio recordings will be pseudo anonymised with participant ID, and at a later stage in the study, the audio files will be renamed to "Parent 1" to destroy the link between the name and the participant ID. After data analysis is completed, data will be deleted and destroyed after two years. Only approved transcriptions services will be used, audio recordings will be transferred from devices onto secure UoM storage as soon as possible following the interview and deleted from the audio recording device.

6.7 Data processing

Clinical collected by the CDS will use paper CRFs, which will be collected by a member of the research team at the time following the clinical assessment. Data from child self-reported questionnaires will be collected directly through a Qualtrics database using an e-tablet. Parental questionnaire data will be collected directly through a Qualtrics database or through postal paper-based questionnaire depending on respondent preference. Questionnaire and CRF data will be entered into the trial database at the Dental Health Unit. Two reminders will be sent to those participants who do not respond within four weeks. All data will be monitored for range, accuracy and consistency.

Data will be securely transferred to the Dental Health Unit for entry into the trial database.

6.8 Change of status / withdrawal procedures

Participants will remain in the trial unless they choose to withdraw consent. All data collected up to the point of complete withdrawal will be retained and used in the analysis.

7 INTERVENTIONS

There will be two trial arms.

The intervention arm will comprise a multi-component intervention consisting of:

- Behaviour change intervention: implementation intention co-produced by the child; educational materials based around COM-B for the family unit (See Appendix A for details of the behaviour change intervention)
- Provision of self-care resources: toothbrush and toothpaste pack every three
 months with plaque disclosing tablet. In line with DBOH recommendations for
 children seven years and upwards, fluoride toothpaste containing fluoride at a
 concentration of 1,350 to 1,500 will be provided. Additional manual
 toothbrushes and 1450 ppm F toothpaste will be supplied for family use every
 three months)
- Educational materials: co-developed curriculum materials, school-based oral
 health promotion incorporating elements of the Colgate-Palmolive Bright Smiles
 Bright Futures materials(BSBF) https://www.colgate.com/en-us/mission/oral-health-commitment/bsbf/educational-resources?bsbf-age-group=age-7-12 (
 See appendix B for BDBF materials)

The comparator arm will be existing school-based oral health education only.

8 SAFETY

18

The sponsor and Chief Investigators have determined this is a low-risk trial and therefore adverse events are unlikely. We will record any adverse events related to the

study e.g. allergic reactions to disclosing tablet/solution. Any Serious Adverse Events will be reported to the Chief Investigator and sponsor. We will also record if the child has had any dental problems/treatments and whether any medication was given.

We do not expect there to be any direct risks for those taking part in the study. The dental assessments are similar to routine dental assessments carried out in clinics. Disclosing tablets/solution contain a food dye called erythrosine and parents/caregivers will be asked if their child is allergic to food dyes.

9 STATISTICS & DATA ANALYSIS

A Detailed Statistical Analyses Plan (SAP) will be produced which will include, but not limited to the investigational plan and study design, listing of outcomes and final analysis of effectiveness. The SAP will set out the summary measures to be reported; methods of analysis, plans for handling missing data, withdrawals, and use of intention to treat analysis.

9.1 Sample size

The typical class size for year 3 children is around 33 children. A sample size of 10 schools in each trial arm with 13 children *per* school (130 children in each group, 260 children in total) would have 90% power to detect a difference of 20% percentage points in plaque scores at 3 months, assuming an intra-school correlation coefficient of 0.03 and an alpha level of 0.05. Assuming an attrition of approximately 15% the total sample size would need to be increased to 306 children, 15 children per school.

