6.6 Quantitative data

Demographic data will be collected from the parent/caregiver on gender, education and employment, and on family membership. Demographic data will be collected on the child's gender, age, ethnic group, and school attended will be collected at baseline. The postcode of the child's main residence will be collected for the purpose of establishing area-level deprivation score, using the Indices of Multiple Deprivation (http://dclgapps.communities..gov.uk/imd/idmap.html). Additionally, information on dental attendance of the child and parent/caregiver will be collected. Demographic information will be collected at baseline either online via online questionnaire (Qualtrics) or on paper once consent has been provided, according to parental/caregiver preference.

Assessments will include the following:

6.6.1 Plaque control record (PCR).

Plaque on tooth surfaces will be collected using the Plaque Control Record (O'Leary, 1972). This is a simple means of recording presence of plaque on individual tooth surfaces calculated as follows: number of surfaces with plaque/number of total tooth surfaces x 100. The clinical examination is non-invasive, utilises a mirror and drying tip. It will also require a plaque disclosing solution which stains the gums and teeth briefly blue or red, which can be removed by brushing. Plaque disclosing is regularly used in dental examinations and can also be used at home and bought in shops. The examination is expected to take no more than 10 minutes per examination. A visual assessment of the presence or absence of plaque on each

surface will then be performed by a member of the Community Dental Service in accordance with the PCR.

- 6.6.2 Toothbrushing habit formation (Parent completed)
 Questionnaire to elicit parental habits around brushing their child's teeth
- 6.6.3 Toothbrushing habit formation (Child completed)
 Questionnaire to elicit child's habit on brushing their own teeth
- 6.6.4 Brief Oral Health Survey (Parent/caregiver completed)
 This questionnaire focuses on parental reported child toothbrushing and sugar consumption, and the value placed by the family on oral health.
- 6.6.4 Brief Oral Health Survey (Parent completed) As above, but for the parent.
- 6.6.5 Brief Oral Health Survey (Child completed) Three questions on brushing behaviour.
- 6.6.6 Brief dental attendance survey (Parent/caregiver completed) This questionnaire focuses on child dental attendance.

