9.2 Statistical analysis

Analyses will be conducted using Stata Statistical Software: Release 18 (StataCorp, College Station, TX, USA) and performed by the study statistician blind to the allocation. An intention-to-treat analysis will be undertaken. Children who changed schools during the course of the trial will be analysed according to their allocation at baseline. Statistical methods to account for the clustering of observations within schools will be used throughout.

Demographic and baseline characteristics will be summarised and displayed in tables for all randomised participants. Frequency counts and percentages will be used to present categorical data. Number of participants, mean, mode, median, SD, minimum, maximum and IQR will be used to present continuous data.

The primary outcome measure will be analysed using a generalised linear model with adjustment for the minimisation variable and baseline value. Secondary outcomes will be analysed using generalised linear models with adjustment for minimisation and baseline variables as appropriate. Statistical significance will be at the 2-sided 5% level and reported along with corresponding 95% confidence intervals derived.

All analyses will be performed on an intention to treat basis. The main statistical

analyses will be based on all participants as randomised, irrespective of subsequent compliance with the trial arm allocation; this will be detailed in the SAP.

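### The 90% power, the 20-point target and the 130 children per arm in Protocol 9.1 agree only if the plaque score has an SD of about 43, which is not stated and is hard to believe on a 0-100 score

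*Protocol*

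**What the plan says.** Section 9.1 sets the design as "A sample size of 10 schools in each trial arm with 13 children" in each school, that is "130 children in each group, 260 children in total". It states that this "would have 90% power to detect a difference of 20% percentage points in plaque scores at 3 months". The ICC behind that statement is 0.03 and the alpha level is 0.05. It gives no SD, no expected mean in either arm and no pair of proportions.

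Section 6.6.1 defines the Plaque Control Record for a child as "number of surfaces with plaque/number of total tooth surfaces x 100", so the outcome is a score from 0 to 100. Section 2.3 takes the primary outcome from index teeth and does not say how many.

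Section 9.2 fixes the analysis: "The primary outcome measure will be analysed using a generalised linear model with adjustment for the minimisation variable and baseline value". It adds "Statistical significance will be at the 2-sided 5% level". Section 9 leaves summary measures, analysis methods, missing data, withdrawals and intention to treat to the SAP. The sample size justification is not on that list; the protocol settles it in 9.1.

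**The concern.** Power for a difference in means depends on the ratio of the difference to the SD. Section 9.1 gives the difference, the numbers, the ICC, the alpha level and the power, so the SD is the only missing quantity and can be solved for. If the answer is implausible for the outcome, the stated figures do not belong together.

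The wording of the target adds doubt. A percent sign followed by percentage points may be a redundant symbol, or a relative reduction may have been meant.

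The target difference is the benchmark against which a null or small result will be read. A reader of 9.1 would take 20 points to be roughly the smallest difference the trial can find with 90% power. If the design can find clearly smaller differences, that reading is wrong. If a relative 20% was meant, the real target is smaller than the one printed.

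**Working it through.** **Inputs from the protocol.** 10 schools per arm, 13 children per school, ICC 0.03, alpha 0.05, power 90% and a difference of 20 (9.1); two-sided test (9.2); score from 0 to 100 (6.6.1). The SD is not given, so the 90% cannot be reproduced directly. The check solves for the SD instead.

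**Step 1: effective sample size.** Design effect = 1 + (13 − 1) × 0.03 = 1.36. Effective n per arm = 130 / 1.36 = 95.6.

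**Step 2: detectable standardised difference.** d = (1.960 + 1.282) × √(2 / 95.6) = 0.469. With a t distribution on 18 degrees of freedom (20 schools minus 2), d = 0.496.

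**Step 3: implied SD.** 20 / 0.469 = 42.7 points; with t, 20 / 0.496 = 40.3 points. Other settings do not bring it down:

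| Variant | Implied SD |
|---|---|
| Two-sided, 90%, normal | 42.7 |
| Two-sided, 90%, t on 18 df | 40.3 |
| One-sided, 90% | 47.2 |
| Two-sided, 80% | 49.4 |
| Two-sided, 90%, no design effect | 49.7 |

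**Step 4: is 42.7 plausible?** A 0-100 score with mean m has a maximum SD of √(m(100 − m)). The overall maximum is 50, with half the children at 0 and half at 100. An SD of 42.7 is possible only if the mean lies between about 24 and 76. A uniform spread has SD 100/√12 = 28.9. A symmetric beta distribution with SD 42.7 puts about 69% of children below 10 or above 90. Baseline adjustment reduces the SD that matters to the residual SD, so if 42.7 were that residual SD, the raw SD would have to be larger still.

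**Step 5: what the design does at other SDs.** These SDs are assumptions. Power = Φ(20 / (SD × √(2/95.6)) − 1.960). Detectable difference at 90% power = 0.469 × SD, or 0.496 × SD with t.

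| Assumed SD | Power for 20 points (normal) | Detectable difference, normal | Detectable difference, t on 18 df |
|---|---|---|---|
| 20 | >99.9% | 9.4 | 9.9 |
| 25 | 99.98% | 11.7 | 12.4 |
| 30 | 99.6% | 14.1 | 14.9 |
| 35 | 97.7% | 16.4 | 17.4 |
| 40 | 93.3% | 18.8 | 19.8 |
| 43 | 89.5% | 20.2 | 21.3 |

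**Step 6: other readings that would give the same size.**

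- *Relative 20% reduction.* A comparator mean of 50, 60 or 70 gives a difference of 10, 12 or 14 points. Dividing by 0.469 gives implied SDs of 21.3, 25.6 and 29.9.
- *Two proportions of children.* 85% against 65%, with unpooled variance, needs 93.3 per arm before clustering. Per school this is 93.3 × 0.97 / (10 − 93.3 × 0.03) = 12.6, which rounds up to 13. Other pairs 20 points apart do not fit: 80% against 60% gives 14.9, 90% against 70% gives 10.0, and 70% against 50% gives 18.4.

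Both readings need inputs that the protocol does not contain.

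**The case against.** The strongest reply is that nothing has been shown to be wrong. With no SD stated, the 90% can be neither reproduced nor refuted, and 43 is below the maximum of 50. The team may have chosen a very cautious SD and meant exactly 20 absolute points. This stands as far as it goes. A reader might infer that the target or its unit must be an error, and the protocol does not prove that.

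The unit also has an ordinary explanation. The score is itself a percentage, so percentage points are its natural absolute unit and the extra sign may be a slip. No other text supports a relative reading. That makes the absolute reading the likelier one, but it is also the reading that needs the SD of about 43.

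The score comes from an unstated number of index teeth. Fewer surfaces make a coarser and more variable score, so the uniform SD of 28.9 should not be treated as a ceiling. That is why the range above runs past it to 35 and beyond. It does not establish an SD of 43.

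The two alternative readings in step 6 fit because their inputs were chosen to fit. A reader might infer that the outcome was sized as yes/no per child and should be redefined that way. Sections 1.1, 2.3 and 6.6.1 consistently describe a plaque score, so they give no ground for changing the outcome.

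Finally, at any SD below about 43 (40 with t) the stated power errs on the safe side. This is correct, and it limits the severity.

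**Conclusion.** Read as absolute points, the power, target difference and size in 9.1 fit together only at an SD of about 43 (40 with t on 18 degrees of freedom). That SD is possible but implausible for this score, and more so after baseline adjustment. At assumed SDs of 20 to 35, power for 20 points is 97.7% or higher, and 90% power is reached at about 9 to 16 points (10 to 17 with t).

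The result rests on the protocol's ICC of 0.03, equal clusters of 13, a two-sided 5% test and the assumed SDs. The protocol does not show whether the cause is a very large assumed SD, a relative 20%, or a formula for two proportions applied to a continuous score.

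Two stronger conclusions should be avoided. The trial is not shown to be short of children; for 20 points it is more likely over-powered. Nor can it be said in general to detect half the stated difference: that holds only near an SD of 20, and at 35 the figure is 16.4 of 20 points, or 82%.

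Severity: should be fixed. The stated power is one the design very probably does not have, but the error is probably conservative and conduct of the trial is unaffected.

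**What to change.** In section 9.1:

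- Give the target difference in absolute Plaque Control Record points only, with the reason for choosing it.
- State the assumed SD, its source, and whether it is the raw SD or the SD after baseline adjustment.
- Recompute with a cluster formula for two means, and name the formula.
- Restate either the power for the chosen target or the detectable difference for 130 analysed children per arm. At ICC 0.03 and 90% power this is 0.47 SD, or 0.50 SD with t on 18 degrees of freedom, converted to points at the stated SD. The detectable difference describes what the design can do; it does not replace the reason for the target.

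The cost is one recalculation and a rewritten paragraph, and the team must commit to an SD. No schools or children are added, and the continuous primary outcome and its analysis stay as planned.

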9.2 Statistical analysis

Analyses will be conducted using Stata Statistical Software: Release 18 (StataCorp, College Station, TX, USA) and performed by the study statistician blind to the allocation. An intention-to-treat analysis will be undertaken. Children who changed schools during the course of the trial will be analysed according to their allocation at baseline. Statistical methods to account for the clustering of observations within schools will be used throughout.

Demographic and baseline characteristics will be summarised and displayed in tables for all randomised participants. Frequency counts and percentages will be used to present categorical data. Number of participants, mean, mode, median, SD, minimum, maximum and IQR will be used to present continuous data.

The primary outcome measure will be analysed using a generalised linear model with adjustment for the minimisation variable and baseline value. Secondary outcomes will be analysed using generalised linear models with adjustment for minimisation and baseline variables as appropriate. Statistical significance will be at the 2-sided 5% level and reported along with corresponding 95% confidence intervals derived.

All analyses will be performed on an intention to treat basis. The main statistical

analyses will be based on all participants as randomised, irrespective of subsequent compliance with the trial arm allocation; this will be detailed in the SAP.

10 TRIAL MANAGEMENT

Trial management will be carried out within the core research group at the Dental Health Unit at The University of Manchester and led by the Senior Trial Co-Ordinator with support from the Trial Co-Ordinator. The research team will meet formally approximately monthly during the course of the trial with additional interim meetings as required.

11 RESEARCH GOVERNANCE, DATA PROTECTION AND SPONSORSHIP

Ethical Approval for the trial will be secured from The University of Manchester ethics committee. The University of Manchester will act as sponsor. (Trial Registration: ISRCTN73613884).

12 ETHICS AND REGULATORY APPROVALS

The protocol will be reviewed and approved by The University of Manchester. The trial will be conducted according to the principles of Good Clinical Practice provided by Research Governance Guidelines. The ethical considerations around this trial have been carefully thought through. As this is a behavioural and education intervention with toothbrush and toothpaste and plaque disclosing tablets which can be purchased by participants, this has been determined as a low-risk study.

13 QUALITY ASSURANCE

Data monitoring and Quality assurance

The study will be monitored by the research team at the University of Manchester Dental Health Unit, [name] at periodic intervals during the study to ensure the study is being conducted according to Good Clinical Practice Guidelines. A trial master file for the study will be created and maintained during the study. The study will be subject to the audit and monitoring regime of the University of Manchester.

14 FINANCE AND INSURANCE

This study is funded by The University of Manchester via an existing internal research account. Vouchers as a thank you for participation will be purchased using funds from the existing internal research account.

20

15 END OF TRIAL

• The trial will end by August 15th 2026.

16 DATA HANDLING, RECORD KEEPING AND ARCHIVING

Details are provided in the Data Management Plan

17 AUTHORSHIP AND PUBLICATION

Following completion of the study, the results may be published in peer reviewed scientific journals, as an internal report or publications on websites. Participants can request a copy of the study results using the contact details provided on the participant information sheet.
